7.2 Safety/Tolerability

Analyses will be performed for all patients having received at least one dose of study drug (pazopanib). The study will use the CTCAE version 4.0 for reporting of non-hematologic adverse events (<http://ctep.cancer.gov/reporting/ctc.html>) and modified criteria for hematologic adverse events.

8.0 ADVERSE EVENTS

8.1 Experimental Therapy

For the most recent safety update, please refer to the current Investigator’s Brochure or Study Agent Prescribing Information for pazopanib. (https://www.gsksource.com/pharma/content/dam/GlaxoSmithKline/US/en/Prescribing_Information/Votrient/pdf/VOTRIENT-PI-MG.PDF).

8.2 Adverse Event Reporting Requirements

Adverse event (AE) monitoring and reporting is a routine part of every clinical trial and is done to ensure the safety of subjects enrolled in the studies as well as those who will enroll in future studies using similar agents. Data on adverse events will be collected from the time of the initial study treatment through 30 days after the last dose of study treatment or study intervention. Any serious adverse event that occurs more than 30 days

after the last study treatment and is considered related to the study treatment must also be reported. Serious Adverse Events (SAEs) will continue to be followed until:

- Resolution or the symptoms or signs that constitute the serious adverse event return to baseline;
- There is satisfactory explanation other than the study treatment for the changes observed; or
- Death.

The investigator is responsible for the detection, documentation, grading and assignment of attribution of events meeting the criteria and definition of an AE or SAE. The definitions of AEs and SAEs are given below. It is the responsibility of the principal investigator to ensure that all staff involved in the trial is familiar with the content of this section.

Any medical condition or laboratory abnormality with an onset date before initial study treatment administration is considered to be pre-existing in nature. Any known pre-existing conditions that are ongoing at time of study entry should be considered medical history.

All events meeting the criteria and definition of an AE or SAE, as defined in Section 8.3, occurring from the initial study treatment through 30 days following the last dose of the study treatment must be recorded as an adverse event in the patient's source documents and on the CRF regardless of frequency, severity (grade) or assessed relationship to the study treatment.

In addition to new events, any increase in the frequency or severity (i.e., toxicity grade) of a pre-existing condition that occurs after the patient begins study treatment is also considered an adverse event.

8.3 Definitions

8.3.1 Adverse Event

An adverse event (AE) is any untoward medical occurrence in a patient receiving study treatment and which does not necessarily have a causal relationship with this treatment. An AE can be any unfavorable and unintended sign (including an abnormal laboratory finding), symptom, or disease temporally associated with the use of an experimental intervention, whether or not related to the intervention.

8.3.2 Serious Adverse Event

An adverse event is considered "serious" if, in the view of the investigator, it results in any of the following outcomes:

- **Death**
If death results from (progression of) the disease, the disease should be reported as event (SAE) itself.
- **A life-threatening adverse event**
An adverse even is considered 'life-threatening' if, in the view of either the investigator, its occurrence places the patient or subject at immediate risk of death. It does not include an adverse event that, had it occurred in a more severe form, might have caused death.
- **Inpatient hospitalization or prolongation of existing hospitalization for \geq 24 hours.**

- A persistent or significant incapacity or substantial disruption of the ability to conduct normal life functions
- A congenital anomaly/birth defect
- Important medical event
Any event that may not result in death, be life-threatening, or require hospitalization may be considered serious when, based upon appropriate medical judgment, they may jeopardize the patient and may require medical or surgical intervention to prevent one of the outcomes listed in this definition of “Serious Adverse Event”. Examples of such medical events include allergic bronchospasm requiring intensive treatment in an emergency room or at home; convulsions that do not result in inpatient hospitalization or the development of drug dependency or drug abuse.

Previously planned (prior to signing the informed consent form) surgeries should not be reported as SAEs unless the underlying medical condition has worsened during the course of the study. Preplanned hospitalizations or procedures for preexisting conditions that are already recorded in the patient’s medical history at the time of study enrollment should not be considered SAEs. Hospitalization or prolongation of hospitalization without a precipitating clinical AE (for example, for the administration of study therapy or other protocol-required procedure) should not be considered SAEs. However, if the preexisting condition worsened during the course of the study, it should be reported as an SAE.

8.3.3 Expected Adverse Events

An adverse event (AE) is considered “expected” if:

- For approved and marketed drug, such as pazopanib, those adverse events are described in the approved Package Insert (Label).
- In clinical research studies, information on expected adverse events is also summarized in the protocol and in the consent document. See section 9.1 for the list of expected adverse events related to the drug under study.

8.3.4 Unexpected Adverse Event

An adverse event (AE) is considered “unexpected” if it is not described in the Package Insert, Investigator’s Brochure, in published medical literature, in the protocol, or in the informed consent document.

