8.5 Serious Adverse Event Reporting Guidelines

- 8.5.1 The Principal Investigator must be notified within 1 business day of study team's knowledge of any event meeting the criteria and definition of a serious adverse event, regardless of attribution, occurring during the study or within 30 days of the last administration of the study drug.
- 8.5.2 The investigator must report all events meeting the criteria and definition of a serious adverse event(s) that are unexpected and possibly related (definite, probable or possible) to study treatment administration to the local IRB within 7 calendar days if death or life threatening, and within 14 calendar days for all others.
- 8.5.3 All Serious Adverse Events that are unexpected and possibly related (definite, probable or possible) to study treatment administration will be reported to the IRB using the CTO Serious Adverse Event form.
- PI needs to be notified of all SAEs within 1 business day- contact information is below:

[name]
University of Michigan
[name]
[name]
[contact]
[contact]
Email: [contact]
 - The study will comply with the regulations found in 21 CFR 312.32 regarding IND safety reports.

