8.6 Routine Reporting

All other adverse events- such as those that are expected, or are unlikely or definitely not related to the study participation- are to be reported annually as part of regular data submission.

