8.7 Reporting of Unanticipated Problems

There are types of incidents, experiences and outcomes that occur during the conduct of human subjects research that represent unanticipated problems but are not considered adverse events. For example, some unanticipated problems involve social or economic harm instead of the physical or psychological harm associated with adverse events. In other cases, unanticipated problems place subjects or others at increased risk of harm, but no harm occurs.

Upon becoming aware of any incident, experience, or outcome (not related to an adverse event) that may represent an unanticipated problem, the investigator should assess whether the incident, experience, or outcome represents an unanticipated problem. The incident, experience or outcomes is considered unanticipated if it meets all of the following criteria:

1. Unexpected (in terms of nature, severity, or frequency);
2. Related or possibly related to participation in the research; and

3. Suggests that the research places subjects or others at a greater risk of harm than was previously known or recognized.

If the investigator determines that the incident, experience, or outcome represents an unanticipated problem, the investigator must report it to the IRB within 14 calendar days of the study team becoming aware of the problem.

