9.0 DRUG INFORMATION

9.1 Pazopanib

- Brand name: Votrient
- Description: 200 mg capsule-shaped, gray tablets dispensed in bottles with 120 tablets.
- Classification: Inhibitor of multiple tyrosine kinases
- Mode of action: Inhibition of VEGFR (vascular endothelial growth factor receptor), PDGFR (platelet derived growth factor) and c-kit,
- Pharmacokinetics: Pazopanib is routinely administered without food i.e. at least 1 hour before or 2 hours after a meal (https://www.gsksource.com/pharma/content/dam/GlaxoSmithKline/US/en/Prescribing_Information/Votrient/pdf/VOTRIENT-PI-MG.PDF). When thus administered WITHOUT food, pazopanib has a median absolute bioavailability of 21% and mean half-life of 30.9 hours. The median time to peak concentration is 2-4 hours after dose, and repeated daily dosing results in 1-4 fold increase in AUC and Cmax with a daily dose up to 800mg daily. Doses above 800mg daily did not show a consistent increase in AUC and Cmax. Administration with food results in about 2 fold increase in AUC and Cmax. Crushing the tablet also resulted in increased AUC, increased Cmax and decreased Tmax when compared to administration of the tablet as a whole. Based on these observations, it was recommended that pazopanib be administered as a whole tablet 1 hour before or 2 hours after a meal. Additionally, the bioavailability of pazopanib is affected by drugs that increase gastric pH, such as esomeprazole, resulting in reduce plasma concentration of pazopanib.

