Once absorbed, pazopanib is highly bound to albumin (~99%) with no concentration dependence in the 10-100 microgram/milliliter range, and a subsequent small volume of distribution (<40% total body water). It is a substrate for human P-gp and human BCRP transporters, which mediate the efflux of substrates from cells in tissues such as small intestine, blood-brain barrier, testes and liver. Therefore, any factors that influence these transporters will also influence the tissue distribution of pazopanib. Furthermore, pazopanib is not a highly metabolized drug, as evidenced by low concentration of metabolites in vivo (<10% of parent drug concentration), and therefore pazopanib is the active drug and the major circulating species. Pazopanib does have 4 metabolites, GSK1268997, GSK1268992, GSK1071306 and GW700201, of which only GSK1268997 was active with similar inhibition of VEGF-induced endothelial receptors as pazopanib. Primary route of pazopanib metabolism is hepatic, and it is thereby excreted through the feces. Less than 4% of administered dose is excreted renally. CYP3A4 is the major metabolizing enzyme, with minor contributions from CYP1A2 and CYP2C8. Routes of metabolism are mono-

oxygenation, dioxygenation and potential oxygenation of a methyl group to a carboxylic acid. Glucuronidation was also detected in human hepatocytes. Steady-state plasma concentrations were reached by 10 days of repeated dose administration. Pharmacokinetics of pazopanib was otherwise not affected by age, race, gender, body weight and creatinine clearance.

- Side effects: Please refer to pazopanib's package insert (https://www.gsksource.com/pharma/content/dam/GlaxoSmithKline/US/en/Prescribing_Information/Votrient/pdf/VOTRIENT-PI-MG.PDF) for a comprehensive list of adverse events.

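### Expectedness has no severity or specificity test, so a related SAE that is a worse form of a listed toxicity has no 7- or 14-day IRB route

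*Combined protocol and SAP*

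**What the plan says.** **What counts as unexpected.** Section 8.3.4 makes an event unexpected "if it is not described in the Package Insert", the Investigator's Brochure, "in published medical literature, in the protocol, or in the informed consent document". Section 8.3.3 makes an event expected once the approved label describes it. It then points to section 9.1 for the list of expected events, but 9.1 holds no list and refers on to the package insert "for a comprehensive list of adverse events".

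**What follows from it.** Section 8.5.2 requires the investigator to report SAEs "that are unexpected and possibly related (definite, probable or possible) to study treatment administration to the local IRB within 7 calendar days" if fatal or life-threatening, and within 14 days otherwise. Section 8.5.3 repeats the two conditions. Under 8.6 the remaining adverse events, with expected ones named as an example, "are to be reported annually as part of regular data submission".

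**A fuller test, elsewhere.** Section 8.7 has the criterion "Unexpected (in terms of nature, severity, or frequency"), but it covers only incidents unrelated to an adverse event.

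**Exposure.** Section 9.1 states: "Administration with food results in about 2 fold increase in AUC and Cmax". Section 1.1 says it is not clear whether this carries over to repeated daily dosing with food.

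**The concern.** The primary objective is the safety of a drug with well-described toxicities, given in a way meant to raise absorption. The main hazard is therefore a known toxicity in a worse form, rather than a new kind of event. Section 1.2 recognises the potential for greater toxicity. A definition that asks only whether an event has been described cannot detect that hazard.

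At stake is how soon the IRB hears. Accrual is planned over 12 months (11.2). If annual reporting runs from the start of accrual, which is an assumption, the first report could arrive when all 16 patients are enrolled.

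**Working it through.** There is no planned figure to reproduce, because the point turns on a definition and a reporting route. Two side calculations bear on its weight.

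**1. The route of one event.** Take a related, life-threatening SAE that is a worse form of a toxicity in the label.

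- 8.3.3 and 8.3.4: it is described, so it is expected. Severity is not consulted.
- 8.5.2 and 8.5.3: it is related but not unexpected. Both conditions are needed, so neither the 7-day nor the 14-day clock starts.
- 8.6: as an expected event, it goes to annual reporting.
- 8.7: severity would count here, but adverse events are outside its scope.

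Mention in the protocol widens the effect. Tables 3 and 4 in section 5.2 name malignant hypertension, posterior reversible encephalopathy syndrome, grade 3 or 4 bleeding, arterial thrombosis, and gastrointestinal fistula or perforation. Read literally, being named there is enough to keep each of them from being unexpected.

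**2. How far exposure exceeds the labelled regimen.** Inputs: a 2-fold food effect (9.1), the dose levels in Table 1, and conventional dosing of 800 mg without food (1.1). Ratio to 800 mg fasted = 2 × dose / 800.

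| Dose with low-fat meal | Ratio to 800 mg fasted |
|---|---|
| 200 mg | 2 × 200 / 800 = 0.5 |
| 400 mg (start) | 2 × 400 / 800 = 1.0 |
| 600 mg | 2 × 600 / 800 = 1.5 |
| 800 mg | 2 × 800 / 800 = 2.0 |

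The single-dose crossover study described in section 1.1 compared 800 mg fed with 800 mg fasted, so the last row is that study's direct contrast. The other rows assume dose-proportionality. All four assume that the single-dose effect persists.

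**3. The interim rule as a backstop.** Section 11.1 pauses the study if more than 5 of 8 patients have a qualifying toxicity, whether or not it is expected. With true rate p, the pause probability is P(X ≥ 6), X ~ Binomial(8, p).

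| True rate p | P(pause) |
|---|---|
| 30% | 1.1% |
| 40% | 5.0% |
| 50% | 14.5% |
| 60% | 31.5% |
| 70% | 55.2% |
| 80% | 79.7% |

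**4. Can frequency be judged event by event?** Take a described event with a true rate of 12%, the sum of the 10% grade 3 and 2% grade 4 ALT increases in Appendix 3. The value serves only to show sampling noise. With X ~ Binomial(16, p), P(X ≥ 4) is 11.6% if the rate stays at 12% and 55.8% if it is 24%. Even the complete trial separates the two poorly, and a single SAE on a 7- or 14-day clock cannot.

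**The case against.** The best case against the point is that the definition is not the only protection.

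- **Other channels.** The principal investigator is told of every SAE within 1 business day regardless of attribution (8.5.1). The study committee meets at least quarterly and the DSMB receives quarterly reports (12.0). This stands: a reader might infer that such events go unseen for a year, and the documents do not support that. The study committee, however, consists of the investigators and study team, and none of these steps is IRB reporting.
- **The interim pause.** It counts expected events, and restarting at a lower starting dose needs IRB approval. This also stands, so annual reporting is not the only way the IRB could learn of a problem. It responds only to very high rates.
- **The regulatory commitment.** Section 8.5 promises compliance with 21 CFR 312.32. It would be too strong to say that no expedited reporting could ever be triggered. But the protocol does not reproduce that regulation's definition or tie it to 8.3.4, so it does not repair the IRB rule in 8.5.2.
- **Wording of 8.6.** It speaks of regular data submission and does not name the IRB. That the IRB hears annually is a reasonable inference rather than stated text.

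Two stronger readings should be resisted. One is that patients generally receive double the labelled exposure; the table above shows this only at 800 mg fed, under its assumptions. The other is to size the gap by doubling the grade 3–4 ALT rate in Appendix 3. The expedited route is for SAEs, a laboratory grade is not an SAE unless it meets a criterion in 8.3.2, and nothing in the protocol turns a 2-fold exposure into a 2-fold event rate.

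**Conclusion.** The point holds as a narrow gap in safety reporting. Under the protocol's own text, a related SAE that is a more severe or more specific form of a described toxicity is not unexpected and has no 7- or 14-day IRB route. The other channels limit the consequence without correcting the definition.

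The number of reports affected cannot be estimated, because the documents give no SAE rate for this regimen. No endpoint, sample size or analysis is touched. The conclusion rests on the natural reading of 8.3.4, that description in any one listed source suffices, and not on any particular size of food effect. It is worth correcting because the trial's main question is safety and the change is small.

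**What to change.** Amend 8.3.3 and 8.3.4 so that an adverse event is unexpected if its nature, specificity or severity is not consistent with one named reference, the package insert, which describes dosing without food. State that mention in the published literature, the protocol or the consent document does not by itself make an event expected. Bring 8.5.2, 8.5.3 and 8.6 into line, and correct the pointer in 8.3.3 to a list that 9.1 does not contain.

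Treat increased frequency separately. Assess it in aggregate at the study committee and DSMB reviews already set up in 12.0, with prompt IRB notification if a review finds an increase, rather than asking the investigator to decide it SAE by SAE.

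The cost is protocol wording and probably a few more expedited IRB reports. Dosing, sample size and analysis are unaffected.

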8.4 Adverse Event Characteristics

8.4.1 CTCAE Term

(AE description) and grade: The descriptions and grading scales found in the NCI Common Terminology Criteria for Adverse Events (CTCAE) version 4.0 will be utilized for AE reporting. All appropriate treatment areas should have access to a copy of the CTCAE version 4.0. A copy of the CTCAE version 4.0 can be downloaded from the CTEP web site. (<http://ctep.cancer.gov>)

8.4.2 Attribution of the AE

The investigator or co-investigator is responsible for assignment of attribution.

Definite – The AE *is clearly related* to the study treatment.

Probable – The AE *is likely related* to the study treatment.

Possible – The AE *may be related* to the study treatment.

Unlikely – The AE *is doubtfully related* to the study treatment.

Unrelated – The AE *is clearly NOT related* to the study treatment.

8.5 Serious Adverse Event Reporting Guidelines

- 8.5.1 The Principal Investigator must be notified within 1 business day of study team's knowledge of any event meeting the criteria and definition of a serious adverse event, regardless of attribution, occurring during the study or within 30 days of the last administration of the study drug.
- 8.5.2 The investigator must report all events meeting the criteria and definition of a serious adverse event(s) that are unexpected and possibly related (definite, probable or possible) to study treatment administration to the local IRB within 7 calendar days if death or life threatening, and within 14 calendar days for all others.
- 8.5.3 All Serious Adverse Events that are unexpected and possibly related (definite, probable or possible) to study treatment administration will be reported to the IRB using the CTO Serious Adverse Event form.
- PI needs to be notified of all SAEs within 1 business day- contact information is below:

[name]
University of Michigan
[name]
[name]
[contact]
[contact]
Email: [contact]
 - The study will comply with the regulations found in 21 CFR 312.32 regarding IND safety reports.

8.6 Routine Reporting

All other adverse events- such as those that are expected, or are unlikely or definitely not related to the study participation- are to be reported annually as part of regular data submission.

8.7 Reporting of Unanticipated Problems

There are types of incidents, experiences and outcomes that occur during the conduct of human subjects research that represent unanticipated problems but are not considered adverse events. For example, some unanticipated problems involve social or economic harm instead of the physical or psychological harm associated with adverse events. In other cases, unanticipated problems place subjects or others at increased risk of harm, but no harm occurs.

Upon becoming aware of any incident, experience, or outcome (not related to an adverse event) that may represent an unanticipated problem, the investigator should assess whether the incident, experience, or outcome represents an unanticipated problem. The incident, experience or outcomes is considered unanticipated if it meets all of the following criteria:

1. Unexpected (in terms of nature, severity, or frequency);
2. Related or possibly related to participation in the research; and

3. Suggests that the research places subjects or others at a greater risk of harm than was previously known or recognized.

If the investigator determines that the incident, experience, or outcome represents an unanticipated problem, the investigator must report it to the IRB within 14 calendar days of the study team becoming aware of the problem.

8.8 Stopping Rules for the Study at Interim Analysis

- Please refer to section 11

9.0 DRUG INFORMATION

9.1 Pazopanib

- Brand name: Votrient
- Description: 200 mg capsule-shaped, gray tablets dispensed in bottles with 120 tablets.
- Classification: Inhibitor of multiple tyrosine kinases
- Mode of action: Inhibition of VEGFR (vascular endothelial growth factor receptor), PDGFR (platelet derived growth factor) and c-kit,
- Pharmacokinetics: Pazopanib is routinely administered without food i.e. at least 1 hour before or 2 hours after a meal (https://www.gsksource.com/pharma/content/dam/GlaxoSmithKline/US/en/Prescribing_Information/Votrient/pdf/VOTRIENT-PI-MG.PDF). When thus administered WITHOUT food, pazopanib has a median absolute bioavailability of 21% and mean half-life of 30.9 hours. The median time to peak concentration is 2-4 hours after dose, and repeated daily dosing results in 1-4 fold increase in AUC and Cmax with a daily dose up to 800mg daily. Doses above 800mg daily did not show a consistent increase in AUC and Cmax. Administration with food results in about 2 fold increase in AUC and Cmax. Crushing the tablet also resulted in increased AUC, increased Cmax and decreased Tmax when compared to administration of the tablet as a whole. Based on these observations, it was recommended that pazopanib be administered as a whole tablet 1 hour before or 2 hours after a meal. Additionally, the bioavailability of pazopanib is affected by drugs that increase gastric pH, such as esomeprazole, resulting in reduce plasma concentration of pazopanib.

Once absorbed, pazopanib is highly bound to albumin (~99%) with no concentration dependence in the 10-100 microgram/milliliter range, and a subsequent small volume of distribution (<40% total body water). It is a substrate for human P-gp and human BCRP transporters, which mediate the efflux of substrates from cells in tissues such as small intestine, blood-brain barrier, testes and liver. Therefore, any factors that influence these transporters will also influence the tissue distribution of pazopanib. Furthermore, pazopanib is not a highly metabolized drug, as evidenced by low concentration of metabolites in vivo (<10% of parent drug concentration), and therefore pazopanib is the active drug and the major circulating species. Pazopanib does have 4 metabolites, GSK1268997, GSK1268992, GSK1071306 and GW700201, of which only GSK1268997 was active with similar inhibition of VEGF-induced endothelial receptors as pazopanib. Primary route of pazopanib metabolism is hepatic, and it is thereby excreted through the feces. Less than 4% of administered dose is excreted renally. CYP3A4 is the major metabolizing enzyme, with minor contributions from CYP1A2 and CYP2C8. Routes of metabolism are mono-

oxygenation, dioxygenation and potential oxygenation of a methyl group to a carboxylic acid. Glucuronidation was also detected in human hepatocytes. Steady-state plasma concentrations were reached by 10 days of repeated dose administration. Pharmacokinetics of pazopanib was otherwise not affected by age, race, gender, body weight and creatinine clearance.

- Side effects: Please refer to pazopanib's package insert (https://www.gsksource.com/pharma/content/dam/GlaxoSmithKline/US/en/Prescribing_Information/Votrient/pdf/VOTRIENT-PI-MG.PDF) for a comprehensive list of adverse events.
- **Drug Interactions:** Strong inhibitors of CYP3A4, P-glycoprotein (P-gp) and Breast Cancer Resistance Protein (BCRP), all three of which include pazopanib as a substrate, should be avoided due to risk of increased toxicity associated elevated levels of pazopanib. Ketoconazole is an inhibitor of both CYP3A4 and P-gp. Lapatinib is a weak inhibitor of CYP3A4, Pgp and BCRP, and has been shown to increase pazopanib concentrations. Examples of strong CYP3A4 inhibitors are itraconazole, clarithromycin, atazanavir, indinavir, nefazodone, nelfinavir, ritonavir, saquinavir, telithromycin, voriconazole. Grapefruit juice may also increase plasma levels of pazopanib through the same mechanism. Strong CYP3A4 inhibitors should be avoided.

On the other hand, CYP3A4 inducers, such as rifampin, may decrease pazopanib plasma levels, and therefore an alternative medication to rifampin is also recommended. *In vitro* studies showed pazopanib inhibited CYP enzymes 1A2, 3A4, 2B6, 2C8, 2C9, 2C19, 2E1 and potentially induced CYP3A4. Pazopanib 800mg daily has no clinically relevant effect on pharmacokinetics of caffeine (CYP1A2), warfarin (CYP2C9 substrate) or omeprazole (CYP2C19 substrate) in clinical pharmacology studies. Concomitant administration of pazopanib with midazolam (CYP3A4 substrate) and dextromethorphan (CYP2D6 substrate) resulted in an increase in the AUC and C_{max}, and increase in urine dextromethorphan to dextrorphan concentrations, respectively. Pazopanib also increased the AUC and C_{max} of paclitaxel when administered concurrently.

Pazopanib is also a potent inhibitor of UGT1A1 and OATP1B1, and therefore may increase the concentrations of drugs primarily metabolized by these enzymes. One such drug is irinotecan, which also has an active metabolite, SN-38, that is metabolized by OATP1B1 and several UGT enzymes. Co-administration of irinotecan and pazopanib resulted in increased concentrations of irinotecan and its active metabolite SN-38.

- Storage and stability: Pazopanib should be stored at room temperature between 20 and 25 degrees Celsius, with excursions permitted to 15 to 30 degrees Celsius.
- Preparation and Dispensing: Pazopanib is dispensed in a bottle and may be repackaged to a pill dispenser bottle.
- Administration:
 - Pazopanib will be administered with a **low-fat meal, defined as a meal containing less than 400 calories and less than 20% fat or 10 grams per meal**, once daily orally.
 - All pazopanib pills for the day must be taken together.
 - Patient compliance with drug administration will be assessed at each visit through a pill diary that will record rate, time of pazopanib intake, number of pills, and if low fat meal was eaten.

- Availability: commercially available
- Return and Retention of Study Drug: Patients may keep their supply of pazopanib as it will not be supplied by the study. They should dispose of any unused pazopanib after their therapy course is complete or if their supply has expired by returning it to their local pharmacy. It should not be thrown in household garbage or disposed of in wastewater
- Drug Accountability: None, pazopanib is a current standard of care for metastatic renal cell carcinoma and therefore will be billed and provided as such.

10.0 Correlatives:

Pharmacokinetics:

A published, validated assay has been established at the Pharmacokinetics Core, College of Pharmacy at the University of Michigan to determine plasma pazopanib concentrations from these samples⁶.

- Patient to take the whole dose of pazopanib by mouth with low fat meal and record time of intake.
- Blood samples (6 mL drawn in EDTA tube) will be placed on ice and centrifuged within 10 minutes of collection, for 10 minutes at 2,000 x g for fractionation followed by transfer of the top (plasma) layer to a secondary non-breakable cryovials for storage at -80°C until shipment to the PK Core lab.
- Samples will be shipped with dry ice.
- Sample should be shipped (with email notification to [contact]) to Pharmacokinetics Core for analysis:

[name]
University of Michigan

[name]
North Campus Research Complex
[name]
[name].

[contact]

Email: [contact]

- The time points for the PK samples are as follows ((± 15 minutes):

| Day | Timing of PK blood draw |
|----------------|---|
| C1D1 post-dose | +2 hrs |
| C2D1 pre-dose | Once anytime between 0 to -4 hrs |
| C2D1 post-dose | +0.5 hrs, +1 hr, +2 hrs, +3 hrs, +4 hrs |
| C3D1 pre-dose | Once anytime between 0 to -4 hrs |
| C3D1 post-dose | +2 hrs |

